**Stage 1**

Increase in serum creatinine to 150% to 199% (1.5 to 1.99 X increase compared with baseline) or increase of greater than or equal to ( $\geq$ ) 0.3 mg/dl ( $\geq$ 26.4 mmol/l) or Urine output <0.5 ml/kg per hour for > 6 but < 12 hours

**Stage 2**

Increase in serum creatinine to 200% to 299% (2.0 to 2.99 X increase compared with baseline) or Urine output <0.5 ml/kg per hour for > 12 hours but < 24 hours

## Clinical Investigation Plan

	
Stage 3 Increase in serum creatinine to greater than or equal to (<math>\geq</math>) 300% (<math>></math>)3 X increase compared with baseline) or serum creatinine of <math>\geq</math> 4.0 mg/dl (<math>\geq</math>354 mmol/l) with an acute increase of at least 0.5 mg/dl (44 mmol/l) or Urine output <math><</math> 0.3 ml/kg per hour for <math>\geq</math> 24 hours or anuria for <math>\geq</math> 12 hours. Patients receiving renal replacement therapy are considered to meet Stage 3 criteria irrespective of other criteria.
			
Valve Thrombosis (VARC 2)	
Any thrombus attached to or near an implanted valve that occludes part of the blood flow path (as confirmed by imaging), interferes with valve function, or is sufficiently large to warrant treatment.
			
Vascular Access Site and Access-Related Complications (VARC 2)	
Major vascular complications
 
 
• Any aortic dissection, aortic rupture, annulus rupture, left ventricle perforation, or new apical aneurysm/pseudo-aneurysm or
 
• Access site or access-related vascular injury (dissection, stenosis, perforation, rupture, arterio-venous fistula, pseudoaneurysm, hematoma, irreversible nerve injury, compartment syndrome, percutaneous closure device failure) leading to death, life-threatening or major bleeding*, visceral ischaemia or neurological impairment or
 
• Distal embolization (non-cerebral) from a vascular source requiring surgery or resulting in amputation or irreversible end-organ damage or
 
• The use of unplanned endovascular or surgical intervention associated with death, major bleeding, visceral ischaemia or neurological impairment or
 
• Any new ipsilateral lower extremity ischemia documented by patient symptoms, physical exam, and/or decreased or absent blood flow on lower extremity angiogram or
 
• Surgery for access site-related nerve injury or
 
• Permanent access site-related nerve injury
 
 
Minor vascular complications
 
 
• Access site or access-related vascular injury (dissection, stenosis, perforation, rupture, arterio-venous fistula, pseudoaneurysms, hematomas, percutaneous closure device failure) not leading to death, life-threatening or major bleeding*, visceral ischemia or neurological impairment or
 
• Distal embolization treated with embolectomy and/or thrombectomy and not resulting in amputation or irreversible end-organ damage or
 
• Any unplanned endovascular stenting or unplanned surgical intervention not meeting the criteria for a major vascular complication or
 
• Vascular repair or the need for vascular repair (via surgery, ultrasound-guided compression, transcatheter embolization, or stent-graft) or
 
 
Percutaneous closure device failure Failure of a closure device to achieve hemostasis at the arteriotomy site leading to alternative treatment (other than manual compression or adjunctive endovascular ballooning)
			
Prosthetic Valve Stenosis Criteria In conditions of normal or near normal stroke volume (50–70 ml).	Parameter	Normal	Mild Stenosis	Moderate/ severe Stenosis
	Peak velocity (m/s)	less than ( $<$ ) 3	3–4	greater than ( $>$ ) 4
	Mean gradient (mm Hg)	less than ( $<$ ) 20	20–40	greater than ( $>$ ) 40
	Doppler velocity index	greater than or equal to ( $\geq$ ) 0.35	0.35–0.25	less than ( $<$ ) 0.25

### Clinical Investigation Plan

(VARC 2)	Effective orifice area (cm  )	greater than (>) 1.1*	1.1–0.8	less than (<) 0.80
Prosthetic Valve Regurgitation Criteria (VARC 2)	Diastolic flow reversal in the descending aorta (semi-quantitative parameters)			
	Diastolic flow reversal in the descending aorta PW Doppler	Absent or brief early diastolic	Intermediate	Prominent, hodiastolic
	Circumferential extent of paraprosthetic AR	less than (<) 10%	10–29%	greater than or equal (≥) 30%
	Doppler parameters (quantitative)			
	Regurgitant volume (ml/beat)	less than (<) 30%	30–59%	greater than or equal (≥) 60%
	Regurgitant fraction	less than (<) 30%	30–49%	greater than or equal (≥) 50%
	EROA (cm^2)	0.10 cm 	0.10-0.29 cm 	≥0.30 cm 

\* Effective orifice area (EOA) used in this protocol is 1.0 cm^2 for Portico valve of 23mm diameter.

## Clinical Investigation Plan

### APPENDIX III: ADDITIONAL DEFINITIONS

#### Adverse Event (AE)

An adverse event (AE) is any untoward medical occurrence, unintended disease or injury, or untoward clinical signs (including abnormal laboratory findings) in subjects, users or other persons, in the context of a clinical investigation, whether or not related to the investigational medical device.

As part of ISO14155 Section 3.2, the adverse event definition has the following notes:

Note 1: This definition includes events related to the investigational medical device or the comparator.

Note 2: This definition includes events related to the procedures involved.

Note 3: For users or other persons, this definition is restricted to events related to the use of investigational medical devices or comparators.

#### Serious Adverse Event (SAE)

Serious adverse event is an AE that led to any of the following:

- d) Death,
- e) Serious deterioration in the health of the subject, that resulted in any of the following:
  1. Life-threatening illness or injury,
  2. Permanent impairment of a body structure or a body function,
  3. Hospitalization or prolongation of patient hospitalization,
  4. Medical or surgical intervention to prevent life threatening illness or injury or permanent impairment to a body structure or a body function,
  5. Chronic disease
- f) Fetal distress, fetal death or a congenital physical or mental impairment or birth defect.

Note: A planned hospitalization for pre-existing condition, or a procedure required by the CIP, without a serious deterioration in health, is not considered a SAE.

#### Adverse Device Effect (ADE)

An adverse event related to the use of an investigational medical device.

This definition includes adverse events resulting from insufficient or inadequate instructions for use, deployment, implantation, installation, or operation, or any malfunction of the investigational medical device.

This definition includes any event resulting from the use error or from intentional misuse of the investigational medical device.

#### Serious Adverse Device Effect (SADE)

Adverse device effect that has resulted in any of the consequences characteristic of a serious adverse event.

#### Unanticipated Adverse Device Effect (UADE)

## Clinical Investigation Plan

As defined in 21 CFR §812.3, unanticipated adverse device effects (UADE) are defined as any serious adverse effect on health or safety or any life-threatening problem or death caused by, or associated with, a device, if that effect, problem, or death was not previously identified in nature, severity, or degree of incidence in the CIP or application (including a supplementary plan or application), or any other unanticipated serious problem associated with a device that relates to the rights, safety, or welfare of subjects.

### **Anticipated Serious Adverse Device Effect (ASADE)**

Anticipated serious adverse device effect (ASADE) refers to any serious adverse effect on health or safety or any life-threatening problem or death caused by, or associated with, a device, if that effect, problem or death was previously identified in nature, severity, or degree of incidence in the investigational plan or application (including a supplementary plan or application), or any other anticipated serious problem associated with a device that relates to the rights, safety, or welfare of subjects.

### **Unanticipated Serious Adverse Device Effect (USADE)**

Unanticipated serious adverse device effect (USADE) refers to any serious adverse effect on health or safety or any life-threatening problem or death caused by, or associated with, a device, if that effect, problem or death was not previously identified in nature, severity, or degree of incidence in the investigational plan or application (including a supplementary plan or application), or any other unanticipated serious problem associated with a device that relates to the rights, safety, or welfare of subjects.

### **Device Deficiency (DD)**

Device deficiency is defined as any inadequacy in the identity, quality, durability, reliability, usability, safety or performance of an investigational device, including malfunction, use errors or inadequacy in the information supplied by the manufacturer including labeling.

Note 1: The definition includes device deficiencies related to investigational medical device or the comparator.

Note 2: Cyber-security incidents related to the investigational product, shall be reported as device deficiencies

A device malfunction is the failure of an investigational device to perform in accordance with its intended purpose when used in accordance with the instructions for use or CIP, or IB.

## Clinical Investigation Plan

### APPENDIX IV: SURGICAL RISK ASSESSMENT TOOLS

This clinical study requires the use of two surgical risk assessment tools:

1. The Society of Thoracic Surgeons' (STS) risk calculation tools (<http://riskcalc.sts.org/STSWebRiskCalc273/de.aspx>)
2. Euro SCORE II (<http://euroscore.org/calc.html>)

## Clinical Investigation Plan

### APPENDIX V: FRAILTY ASSESSMENT

The Frailty Index will be used as an assessment tool to determine if frailty is a risk factor for subjects prior to enrollment. The assessments will be performed after the informed consent has been obtained and prior to procedure. The assessments can be administered by either an investigator or research coordinator.

The frailty assessment consists of four evaluations:

1. Katz Index of Independence in Activities of Daily Living
2. Grip Strength
3. 5 Meter walk test
4. Serum albumin

#### 1. Katz Index of Independence in Activities of Daily Living Activities

Points (1 or 0)	Independence (1 Point) NO supervision, direction or personal assistance	Dependence (0 Points) WITH supervision, direction, personal assistance or total care
BATHING Points: _____	(1 POINT) Bathes self completely or needs help in bathing only a single part of the body such as the back, genital area or disabled extremity	(0 POINTS) Need help with bathing more than one part of the body, getting in or out of the tub or shower. Requires total bathing
DRESSING Points: _____	(1 POINT) Get clothes from closets and drawers and puts on clothes and outer garments complete with fasteners. May have help tying shoes.	(0 POINTS) Needs help with dressing self or needs to be completely dressed.
TOILETING Points: _____	(1 POINT) Goes to toilet, gets on and off, arranges clothes, cleans genital area without help.	(0 POINTS) Needs help transferring to the toilet, cleaning self or uses bedpan or commode.
TRANSFERRING Points: _____	(1 POINT) Moves in and out of bed or chair unassisted. Mechanical transfer aids are acceptable.	(0 POINTS) Needs help in moving from bed to chair or requires a complete transfer.
CONTINENCE Points: _____	(1 POINT) Exercises complete self control over urination and defecation.	(0 POINTS) Is partially or totally incontinent of bowel or bladder.
FEEDING Points: _____	(1 POINT) Gets food from plate into mouth without help. Preparation of food may be done by another person.	(0 POINTS) Needs partial or total help with feeding or requires parenteral feeding.
TOTAL Points: _____		

#### 2. Grip strength

*Subjects elbow should be at a 90 degree angle without arm supported or resting on table or against chest wall. Each grasp should be completed with the dynamometer in the dominant hand.*

## Clinical Investigation Plan

Grasp 1 \_\_\_\_\_ Grasp 2 \_\_\_\_\_ Grasp3 \_\_\_\_\_ Average \_\_\_\_\_

### Grasp Strength, stratified by gender and body mass index (BMI) quartiles

Gender	BMI	Cutoff for grip strength (Kg) criterion for frailty
Male	≤24	≤29
	24.1–26	≤30
	26.1–28	≤31
	>28	≤32
Female	≤ 23	≤17
	23.1–26	≤17.3
	26.1–29	≤18
	>29	≤21

### 3. 5 Meter Walk Time

*This examination should be performed indoors, along a long, flat, straight, enclosed corridor with a hard surface that is seldom traveled. The walking course must be 5 meters in length (15 feet). The time to walk this distance is to be recorded.*

\_\_\_\_\_seconds

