##### 5.1.1 High Risk Classification

High risk classification will be assigned to subjects with severe aortic stenosis symptoms for whom conventional aortic valve replacement surgery is associated with high risk equivalent to an STS risk score that is  $\geq 7\%$ .

Patients with an STS risk score that is  $< 7\%$  will be assigned high risk if frailty indices and/or existing comorbidities not captured by STS are also present. Specifically, assessments of patient's physical performance including a 15-foot (5m) gait speed test, grip strength testing and Katz Index of Independence in Activities of Daily Living will be considered along with surgical comorbidities not addressed in the STS score (including porcelain aorta, pulmonary hypertension, mitral regurgitation, moderate tricuspid regurgitation, diabetes, chronic kidney disease, chronic and/or oxygen dependent lung disease).

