##### 5.1.2 Extreme Risk Classification

Extreme risk classification will be assigned to subjects with severe aortic stenosis symptoms who are deemed unsuitable for conventional aortic valve replacement because of predicted probability of  $\geq 50\%$  mortality, or at risk for a serious irreversible complication by 30 days.

Subjects with an STS risk score that is  $> 7\%$ , aged  $> 90$  years and with a frailty index  $\geq 2$  will automatically be classified as extreme risk. No more than 20% of subjects ( $n=33$  for the Portico NG cohort and  $n=12$  for the Titan cohort) in the total analysis population or the first 80 subjects ( $n=16$ ) who undergo a Navitor implant attempt may be classified as extreme risk.

---

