## Clinical Investigation Plan

### 5.2 Subject Screening and Informed Consent

#### 5.2.1 Subject Screening

Potential patients presenting at the study sites will be fully informed about the clinical study, following the established Informed Consent process (described in Section 5.2.2). Once a duly dated and signed Informed Consent form is obtained, the clinical study-specific screening procedures may begin. All cardiac medications and all medications given for cardiovascular effect may be continued at their prescribed dosages for the screening assessments.

The following assessments are performed as part of the screening process:

1. Demographics (age on consent date, gender)
2. Medical History (including major cardiovascular, vascular, and other coexisting medical conditions)
3. Physical Exam (including weight, heart rate, blood pressure)
4. Surgical Risk Assessment tools (STS Risk Score and EuroSCORE II)
5. New York Heart Association (NYHA) Functional Classification
6. Frailty Index Assessment (Katz index of Activities of Daily Living, Grip Strength, 5 meter walk test)
7. Forced Expiratory Volume (FEV1) Test, if clinically indicated
8. Echocardiography to include comprehensive transthoracic or transesophageal 2D echocardiogram, including assessment of aortic valve gradients (mean and peak), areas, indices, degree of regurgitation, cardiac output and cardiac index, left ventricle systolic function (global and segmental)
9. Lab Measurements (including CBC and Platelet count, BUN and creatinine, BNP or ProBNP, and Albumin)
10. 12 Lead Electrocardiogram (ECG)
11. Computed Tomography Scan with Angiography for chest, abdomen and pelvis: aortic root and valve annulus sizing, assessment of suitability of iliofemoral or alternate access, and determination of appropriate coaxial angles for optimizing the valve implantation procedure. CT scan performed up to 12 months prior to consent will be acceptable.
12. 3D Transesophageal Echocardiogram (TEE) if CT is contraindicated
13. Coronary and aortic angiogram (arteriograms of the lower abdominal aorta to the femoral arteries), with runoff if clinically indicated. Coronary and aortic angiogram performed up to 12 months prior to consent will be acceptable.
14. Adverse Event Assessment

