### 5.3.2 Inclusion Criteria

#### 5.3.2.1 General Inclusion Criteria

1. Subjects must have a Society of Thoracic Surgeons (STS) score of  $\geq 7\%$  OR documented heart team agreement of high or extreme risk for surgical aortic valve replacement due to frailty or comorbidities not captured by the STS score.
2. Subject is of legal age or older for consent in the host country.
3. Subject has symptomatic aortic stenosis as demonstrated by NYHA Functional Classification of II, III, or IV.
4. The subject has been informed of the nature of the study, agrees to its provisions and has provided written informed consent as approved by the Institutional Review Board (IRB) or Ethics Committee (EC) of the respective clinical site.
5. The subject and the treating physician agree that the subject will return for all required post-procedure follow-up visits.

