### Walk Time, stratified by gender and height

Gender	Height	Cutoff values for Time to Walk 5 meters criterion for frailty
Male	≤ 173 cm	≥ 7sec
	> 173 cm	≥ 6sec
Female	≤159 cm	≥ 7sec
	> 159 cm	≥ 6sec

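### Appendix V and section 5.1.1 equate 5 meters with 15 feet; the lengths differ by 9%, which shifts the speed threshold of one of the four frailty items

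*Protocol*

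**What the plan says.** Appendix V sets the course for the timed walk: "The walking course must be 5 meters in length (15 feet"). Section 5.1.1 lists the same test among the physical-performance measures used to assign high risk when the STS score is below 7%, with the units in reverse order: "15-foot (5m) gait speed test".

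The pass/fail table in Appendix V is headed "Cutoff values for Time to Walk 5 meters criterion for frailty". A patient meets the item at 7 seconds or more in the shorter height group (men up to 173 cm, women up to 159 cm) and at 6 seconds or more in the taller group. Nothing adjusts these times for course length. The screening list in section 5.2.1 names only the metric distance: "Frailty Index Assessment (Katz index of Activities of Daily Living, Grip Strength, 5 meter walk test". The 30-day and 12-month visit lists and Table 5 do the same.

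The result is used as follows.

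- Appendix V: "The frailty assessment consists of four evaluations". The timed walk is one; the others are the Katz index, grip strength and serum albumin.
- Section 5.3.2.1: a subject with STS below 7% can qualify through "documented heart team agreement of high or extreme risk for surgical aortic valve replacement due to frailty or comorbidities not captured by the STS score".
- Section 5.1.2: subjects with STS above 7%, age above 90 years and a frailty index of at least 2 "will automatically be classified as extreme risk".

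**The concern.** A mandatory test instruction gives two lengths as if they were one. For a measure reported only as a number this would be untidy. Here the time is compared with a fixed cut-off, so the length of the course sets the walking speed at which a patient counts as slow. A site following the feet and a site following the meters would apply different thresholds under the same protocol, and both could claim to comply.

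What is at stake is the consistency of one frailty item, and through it, in some patients, the support for a high-risk or extreme-risk classification.

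**Working it through.** **Inputs.** Course length of 5 m, given as 15 ft (Appendix V and section 5.1.1). Cut-offs of 6 s and 7 s (Appendix V walk-time table). Conversion: 1 ft = 0.3048 m exactly.

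**The stated equivalence does not reproduce.**

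- 15 × 0.3048 = 4.572 m
- 5 / 0.3048 = 16.40 ft
- 5 − 4.572 = 0.428 m
- 5 / 4.572 = 1.094, so 5 m is 9.4% longer than 15 ft
- 1 − 4.572 / 5 = 0.086, so 15 ft is 8.6% shorter than 5 m

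Rounding does not explain the gap. To the nearest foot, 5 m is 16 ft (16 × 0.3048 = 4.88 m). The six-minute walk in Appendix XII shows what a reasonable pairing looks like: a 30 m course and a 100-ft hallway, where 100 × 0.3048 = 30.48 m, within 2%.

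**Speed threshold implied by each cut-off** (length / time; the item is met at this speed or slower).

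| Cut-off | On 5 m | On 15 ft |
|---|---|---|
| 6 s | 5 / 6 = 0.833 m/s | 4.572 / 6 = 0.762 m/s |
| 7 s | 5 / 7 = 0.714 m/s | 4.572 / 7 = 0.653 m/s |

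**Who changes category, at constant speed.** Time on 15 ft = time on 5 m × 4.572 / 5 = time on 5 m × 0.9144.

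- A 5 m time of 6.0 s becomes 6.0 × 0.9144 = 5.49 s. The 5 m time that gives exactly 6 s on 15 ft is 6 / 0.9144 = 6.56 s.
- A 5 m time of 7.0 s becomes 7.0 × 0.9144 = 6.40 s. The 5 m time that gives exactly 7 s on 15 ft is 7 / 0.9144 = 7.66 s.

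So patients with a 5 m time from 6.00 to under 6.56 s (taller group) or from 7.00 to under 7.66 s (shorter group) meet the item on 5 m and miss it on 15 ft. The bands are about 0.56 s and 0.66 s wide. The shift goes one way only: the shorter course scores fewer patients as meeting the item.

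**Example.** A patient in the taller group walking at 0.80 m/s takes 5 / 0.80 = 6.25 s on 5 m (item met) and 4.572 / 0.80 = 5.72 s on 15 ft (item not met).

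**What cannot be calculated.** The documents give no distribution of walk times and do not say which length any site used, so neither the number nor the share of patients affected can be derived.

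**The case against.** The strongest reply is that the documents already point to one length. The Appendix V heading, the test name, the screening and follow-up lists and the cut-off table all say 5 meters, and only the narrative in section 5.1.1 puts feet first. On that view, all that remains is a wrong conversion in two places. This largely stands and is the main reason the weight is low. It does not make the text correct, because one of those places is the instruction for laying out the course.

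A second reply is that times may be recorded to the nearest second. In that case the example above gives 6 s on both courses and does not flip. The worksheet states no precision, so this is an assumption, and rounding would move the band without closing it. With an effective cut-off of 5.5 s, the affected 5 m times would run from 5.50 to under 5.5 / 0.9144 = 6.01 s.

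A reader might also infer more than the documents support:

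- **That the same patient becomes frail or not frail overall.** The calculation flips one item of four. It does not by itself change the frailty index.
- **That eligibility turns on the course laid out.** Below STS 7% there is no numeric walk threshold for entry. The heart team weighs gait speed, grip strength and Katz together with comorbidities, and the Subject Selection Committee makes the final determination.
- **That extreme-risk numbers, and so the 20% cap, would move.** The automatic rule also needs STS above 7% and age above 90. If the index counts items met, the walk decides only when exactly one other item is positive. Section 5.1.2 also has a separate route to extreme risk based on predicted mortality or irreversible complication.
- **That US sites would differ from others, or that comparison with published cohorts is distorted.** Nothing says which length any site laid out, and how those cohorts measured frailty cannot be checked from these documents.

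**Conclusion.** The point holds as an error in the text, with low weight. Appendix V and section 5.1.1 equate two lengths that differ by 9%. With fixed cut-offs, the shorter course lowers the speed threshold of the walk item by 8.6%, from 0.83 to 0.76 m/s or from 0.71 to 0.65 m/s.

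Risk class would change only where the item is decisive. That means either as one input to the heart-team and committee judgement when STS is below 7%, or in the automatic extreme-risk rule for a patient who also has STS above 7% and age above 90. The affected bands assume constant walking speed over both distances and times recorded finely enough to compare with the cut-off. The number of patients affected is unknown and could be zero. Neither primary endpoint, nor the test against the 8.5% goal, nor either cohort's success criterion uses walk time directly.

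**What to change.** Reconcile section 5.1.1 and the Appendix V course instruction with the distance that the 6 s and 7 s cut-offs assume. The table heading names 5 meters, and the sponsor should confirm that against the source of the cut-offs. Then state one course length in both places with its correct conversion (5 m = 16.4 ft, or 15 ft = 4.57 m), and notify sites. A CRF field for the distance is unnecessary once a single length is stated.

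The cost is a wording correction in two places and a site memo. If a site reports having used the other length, the walk item may need another look for a few subjects. Converting those times would rest on the constant-speed assumption.
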